5.0 Research Design and Methods

- 5.1 Subject Identification and Recruitment: Potential subjects will be identified through the UW Orthopedics/Sports Medicine and UW Physical Therapy Clinics (Research Park, East and West) and surrounding Sports Medicine clinics. Study staff with UW Health electronic health record (Health Link) access may search patient list templates made available to them as part of their research access to Health Link to help identify potential subjects for study enrollment evaluation. Those that appear to meet eligibility criteria will be introduced to this research opportunity by someone involved in their care. Patients that agree will be contacted by research team personnel to learn more about participation. Recruitment flyers will also be posted in these locations.

The healthy normal subjects will be recruited from the IRB approved database of healthy volunteers (2017-0004, [name], PI). These subjects will be contacted by the database manager either by phone or email and will be provided with information about participation. Those interested in participating will be referred to a study team member to learn more about participation and to be scheduled for an initial study visit.

Recruitment efforts will also include the use of UW campus mass emails, fliers, UW website, social media, and postcards. Flyers will be posted in the UW Sports Medicine Clinics (Research Park and East), UW Physical Therapy Clinics (Research Park, East and West), University Health Services, as well as in sport facilities in the area (Natatorium, SERF, Health Clubs, etc). Recruitment flyers and postcards will also be made available to physical therapists and athletic trainers in the area and at other colleges and universities that provide a letter of support for this research.

Recruitment material will be made available at events such as local fun runs/races. We will also search medical records using ICD9 codes for potential subjects. One mailing will occur to potential subjects, which will include a letter or postcard describing the study. All recruitment material will include a brief summary of the purpose of the research, the number and duration of study visits, the contact information for the research team, and compensation.

5.2 Consent: The consent process will occur prior to administration of research procedures at the baseline visit. Potential subjects will meet with a study team member to review the information in the consent form including study procedures, risks associated with participation, alternatives to participation and whom to contact for additional information. After the subject has provided signed consent, any relevant laboratory tests will be obtained and confirmed prior to final enrollment in the study. Any questions will be addressed prior to the start of any research procedures and all subjects will be reminded that participation is optional and they can change their mind at any time.

During the COVID-19 pandemic, consent procedures will be conducted by phone, when possible, to minimize face-to-face contact subjects have with the research team. A copy of the consent form will be mailed or emailed to subjects prior to the scheduled consent phone call. If emailed, the consent form will be encrypted. A study team member will call potential subjects at the scheduled time to review the information in the consent form including study procedures, risks associated with participation, alternatives to participation and whom to contact for additional information. Any questions will be addressed during the course of the phone call and subjects will be encouraged to contact the study team with any questions or concerns they might have at any time. Upon completion of the consent process, a copy of the signed consent form will be provided in one of the following ways depending on each subject preferences and capabilities:

- Electronic signature will be provided using DocuSign
- Subject will be asked to scan a copy of the entire consent document and email it back to the study team.
- Subject will be asked to take a photo of the signature page and email a copy to the study team.
- If subjects are unable to provide an electronic copy of the signed consent form, they will be asked to bring a copy of the form to the research visit.

5.3 Research Procedures: Subjects enrolled in the chronic PT cohorts will be asked to complete four study visits at baseline, 16 weeks, 32 weeks, and 52 weeks. Subjects enrolled in the control cohort will complete 1 study visit. Health questionnaires (VISA-P Tegner, medication log, side effect log) will be mailed to subjects diagnosed with chronic PT only. A table outlining research visits is below. The following research procedures will be administered:

- 5.3.1 Randomization: The 10 healthy/normal subjects will not be randomized and will not receive any injections. The subjects diagnosed with chronic patellar tendonitis will be randomized to one of three study arms. Subjects in Group 1 (PRP) will receive a single US-guided (USG) injection of 5 mL autologous PRP using a 22G, 1.5 inch needle and after 20 needle passes targeting hypoechoic and hyperemic areas within tendon and bone attachment if involved. Subjects in Group 2 (DN) will undergo USG dry needling with 20 passes using a 22G, 1.5 inch needle targeting hypoechoic and hyperemic areas within tendon and bone attachment if involved. Subjects in Group 3 (SH) will undergo a sham control USG dry needling with 20 passes using a 22G, 1.5 inch needle placed in the subcutaneous tissue only (not intratendon) at the level of the patella tendon.
- 5.3.2 PRP Preparation and Administration (randomized subjects only): At the injection session, a nurse will perform a standard antecubital blood draw (15mL) using a 15 mL syringe and an 18G needle from the PRP group at the contralateral arm. The blood draw will occur only once. The study coordinator will then place the sample in the Arthrex ACP System and spin the blood sample using a two-stage spinning: the 1st separates red blood cells from platelets, and the 2nd concentrates the platelets to yield approximately 6mL of concentrated, autologous platelets. This layer of platelet rich plasma will be placed in the syringe by the centrifuge machine. Centrifuging will be repeated if desired concentration level is not achieved, but this has not occurred clinically and we do not anticipate inadequate platelet concentration level. All blood and equipment handling will follow universal precautions.

Platelet counts from subjects' whole blood and PRP processed blood will be analyzed. Platelet counts in whole blood vary by individual. The optimal quantity of platelets and growth factors required for tissue healing is not known, but a clinically effective concentration has been described as being greater than 4 times baseline autologous whole blood platelet concentrations (Marx RE: Platelet-rich plasma: Evidence to support its use. J Oral Maxillofac Surg 2004;62:489-496.). Therefore, platelet concentration yield may have important implications in clinical outcome correlation. In order to validate consistent platelet concentration yields across subjects, we will sample 1mL of whole blood (approximately one lab Vacutainer) and an additional 1 mL of platelet rich plasma for lab analysis of platelet to be completed by the UWHC Clinical Laboratory. This extra 1 ml of whole blood will be drawn at the same time that the 15 ml described above is drawn. After results are analyzed, the specimens will be discarded into biohazard waste.

The plasma poor platelet portion will be discarded in biohazard waste and destroyed day of procedure. The 5ml of platelet rich plasma will be injected into the subject's PT.

There will be no subject identification number associated with the blood before it is placed in the centrifuge system. It is a closed system. It spins the blood of one subject only. There is no risk of cross contamination.

The specimens will not be kept or stored. The blood will be analyzed on the same day as the procedure is being performed. This will not require storing of the specimen and prevent erroneous labeling of platelet concentration with a different subject.

The skin will be cleansed with an alcohol wipe and Hibicleanse. Lidocaine skin heals will be placed for local analgesia. The Patellar tendinopathy area will be identified using the US 15-6MHz linear array transducer. Under continuous US evaluation, 1 mL of the prepared solution will be injected into the diseased area of the PT itself using a 22G, 1.5" long needle. Then, up to 4.0 mL of the solution will be peppered along a short segment of the tendon into the areas of palpated tenderness and US documented pathology for a total of 5ml. After the injections, the subject will rest for 5 minutes. Participants will be telephoned after 3 days to enquire about side effects or adverse events.

Dry Needling (DN) Procedure: This is a therapeutic procedure that involves the same injection procedures under ultrasound guidance as in the PRP group but no PRP will be injected inside the patellar tendon.

Sham (SH) Placebo Procedure: Same needle size is used under ultrasound guidance as in PRP and DN groups but we will not inject PRP nor place needle inside the patellar tendon. Rather, the needle will be placed in the soft tissue next to the patellar tendon.

- 5.3.3 **Blinding (randomized subjects only):** Subjects and assessors will be blinded to the subject group allocation. Subjects in the DN and SH groups will also undergo phlebotomy to maintain blinding. Subjects will be identified to study personnel using a unique study number only and results of the imaging studies will be blinded, batched, and evaluated in a randomized manner.
- 5.3.4 **Clinical and Biomechanical Assessment (see Appendix A) - All subjects:** The clinical symptoms of all subjects will be assessed using the validated pain- and function-dependent, PT-specific Victorian Institute of Sport Assessment Patella (VISA-P) quality of life score and Tegner activity level scale. Knee flexor and extensor muscle isometric torque strength will be assessed using an isokinetic dynamometer (Kiio Sensor). Patellar tendon wave speeds will be measured with an experimental device during any or all of: strength tests with the Kiio sensor, squats, vertical jumps, walking, and running. The walking/running tasks will only be performed with subjects who have experience with treadmill walking/running. The wave speed measurement device will be placed on the surface of the skin. It consists of a piezoelectric actuator that induces waves in the tendon and miniature accelerometers that track wave propagation.

5.3.5 MRI Protocol: All subjects will undergo a non-contrast MRI examination of the knee on an MR750 3T scanner (GE Healthcare, Waukesha, WI) using an 8-channel extremity coil. Subjects will be in the scanner for approximately 45 minutes.

5.3.6 US Protocol: All subjects will undergo an US examination of the patellar tendon using both LOGIQ E9 (GE Healthcare Waukesha, WI) and Aixplorer (Supersonic Imagine, Aix-en-Provence, France) imaging systems with a 15-6MHz linear array transducer. Use of two US imaging systems will allow comparison of SWS measurements across different vendor platforms, which would be important for repeatability in future large-scale clinical trials. Imaging will take approximately 60 minutes total to complete.

5.3.6 Review of Medical Records (All subjects):
The following information will be collected from the randomized subjects: Patient age, height, weight, history of PT pain, duration of symptom related to PT, past medical history, past surgical history, medication history and current use, medication allergy.
The following information will be collected from the healthy/normal subjects: Patient name, height and weight, phone number, lifestyle and health history.

*Randomized subjects only

Procedure	Measurements	Assessment Time (weeks)			
		0	16*	32*	52*
Signed Consent and Randomization		✓			
PRP Procedure*	Collection, processing and administration	✓			
VISA-P Tegner*	Pain and function score of PT	✓	✓	✓	✓
Symptoms/Biomechanics	Knee Strength testing	✓	✓		✓
MRI	Single/bi-component UTE-T2*, PT volume	✓	✓		✓
Conventional US	PT thickness, echogenicity, hyperemia	✓	✓		✓
SWI	SWS measurements	✓	✓		✓
Medication/PT Log*	Pain medicine use, eccentric exercise adherence	✓	✓	✓	✓
Side Effects Log*	Side effects	✓	✓	✓	✓
Exit Interview	Satisfaction score, qualitative assessment of study experience				✓

5.4 Risks

- 5.4.1 PRP Preparation and Administration: The main risk associated with this process is temporary pain and swelling during the phlebotomy procedure to collect the sample and at the injection site during the treatment phase. Sterile technique will be employed during all phases of this process which will minimize any opportunity for the sample to be contaminated or the collection/injection site to be infected.
- 5.4.2 MR Imaging: The risk from a non-contrast enhanced MRI exam is minimal and is primarily related to claustrophobia and discomfort with positioning. Thorough screening will be completed to ensure subjects with contraindications to MR are identified. Only qualified staff will be involved with conducting the MR exam.
- 5.4.3 US Imaging: There are no physical risks associated with US imaging.
- 5.4.4 Subjects could injure themselves by stumbling or falling while walking or running on the motorized treadmill. These tasks will be familiar to subjects who are asked to perform them, so the risks are relatively minor. Additionally, there is a risk of minor skin irritation from the wave speed measurement device.

5.5 Benefits: There are no benefits expected for the study participant. However, positive outcomes from this study would establish an effective non-surgical treatment option for PT and demonstrate that disease modification of PRP-treated PT with clinical improvements in pain and knee strength is directly related to improvements in the imaging features of the healing tendon.

5.6 Criteria for Removal from Study: Enrolled patients will be removed from the study in the following circumstances:

- The patient is unable to complete all research procedures
- The subject withdraws consent

- Exclusion criteria are discovered after informed consent has been obtained but prior to the research examination.

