4.0 SELECTION OF PATIENTS

- 4.1 Study Population: This research will enroll 10 healthy normal adults and 66 adults diagnosed with chronic patellar tendonitis.
- 4.2 Eligibility criteria (healthy/normal)
 - 4.2.1 Age between 18 and 39 years
 - 4.2.2
- 4.3 Eligibility criteria (Subjects diagnosed with chronic patellar tendonitis)
 - 4.3.1 Inclusion criteria
 - 4.3.1.1 Age between 18 and 39 years
 - 4.3.1.2 Chronic (>3 months) PT
 - 4.3.1.3 Clinical examination consistent with PT
 - 4.3.1.4 MRI or US confirmation of PT
 - 4.3.1.5 Pain score of 3 or greater on a 10-point VAS
 - 4.3.1.6 Self-report failure of supervised physical therapy

- 4.3.1.7 Self-report failure of at least 2 of the most common treatment options for PT (e.g. NSAIDs, relative rest, ice and bracing).
- 4.3.2 Exclusion criteria (All subjects)
 - 4.3.2.1 Inability to comply with study follow-up requirements
 - 4.3.2.2 History of bleeding disorders or other hematologic conditions
 - 4.3.2.3 Knee pain from other possible etiologies (e.g., degenerative joint disease, meniscal tear, ligament injury or reconstruction)
 - 4.3.2.4 Full or partial patellar tendon tear
 - 4.3.2.5 Current use of anticoagulation or immunosuppressive therapy
 - 4.3.2.6 Prior knee trauma requiring medical attention or surgery
 - 4.3.2.7 Self-reported pregnancy
 - 4.3.2.8 Worker's compensation injury
 - 4.3.2.9 Daily opioid use for pain
 - 4.3.2.10 Contraindication to MRI.
 - 4.3.2.11 Systemic diseases such as Diabetes and connective tissue diseases.
 - 4.3.2.12 Prior PRP or DN procedure.
 - 4.3.2.13 Women that are pregnant

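### Section 5.6, read literally, removes a treated patient who cannot do a week 16 test, and the later VISA-P scores and side effect logs could be lost with that patient

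*Combined protocol and SAP*

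**What the plan says.** Section 5.6 opens with "Enrolled patients will be removed from the study in the following circumstances". Its first bullet reads "The patient is unable to complete all research procedures". It names no visit, lists no essential procedures and makes no exception. The third bullet, by contrast, carries a time limit: "Exclusion criteria are discovered after informed consent has been obtained but prior to the research examination".

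The visit table in Section 5.3 puts "Knee Strength testing", MRI and ultrasound at weeks 0, 16 and 52. VISA-P/Tegner and the medication and side effect logs are due at weeks 0, 16, 32 and 52, and at week 32 nothing else is listed. Section 5.3 also states: "Health questionnaires (VISA-P Tegner, medication log, side effect log) will be mailed to subjects diagnosed with chronic PT only". It does not say for which weeks.

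Treatment is one baseline session. In the PRP arm, for example, subjects "will receive a single US-guided (USG) injection of 5 mL autologous PRP" (5.3.1).

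Section 8.0 bases the sample size on VISA-P change over one year, with 20 subjects per group and 22 recruited to allow for 10% dropout. It names no analysis model and does not say how a removed patient is handled. Section 7.0 covers storage of collected data but not their analysis.

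**The concern.** Treatment is over after the baseline session, so removal at week 16 withdraws no study treatment. All it can do is end follow-up. The documents do not say that questionnaires stop on removal, but that is the natural meaning, and nothing provides for continuing them. What could be lost is the measure that the sample size rests on, together with late side effect reports, because of a test that neither depends on.

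Whether this causes more than a loss of precision depends on why the patient could not do the test. Appendix A asks for maximal knee extension on the involved limb and takes a pain score afterwards. If pain stopped a patient from completing that test, the loss would be related to VISA-P, which itself measures pain and function. Should such losses differ between arms, the week 52 contrast would be biased. MRI intolerance has no evident link to VISA-P.

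**Working it through.** **1. Does the literal reading reach a treated patient?**

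- Section 5.3 introduces its list as the research procedures, and strength testing (5.3.4), MRI (5.3.5) and ultrasound (5.3.6) are on it.
- The table repeats all three at week 16, after treatment.
- The first bullet of 5.6 is not limited to the period before treatment; the third bullet is limited to before the research examination.
- No section keeps a removed patient in follow-up.

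So the literal reading does reach such a patient. Inability that first arises at week 16 puts the week 32 and 52 VISA-P at risk. Inability that first arises at week 52 costs no later VISA-P.

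**2. The plan's own figures.** Recruitment: 20 × 1.10 = 22 per group, an allowance of 2 per arm. The two Table 2 rows used here reproduce with a one-way ANOVA F test (noncentral F; alpha is not stated, 0.05 assumed). Means of 5.5, 5.5 and 22 have grand mean 11, so the squared deviations sum to 30.25 + 30.25 + 121 = 181.5, and the noncentrality is n × 181.5 / SD².

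- SD 20, n = 20: 20 × 181.5 / 400 = 9.08, power 75.1% (stated 75.1%).
- SD 15, n = 20: 20 × 181.5 / 225 = 16.13, power 94.8% (stated 94.8%).

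**3. Precision.** If removals fall inside the 10% allowance, n stays at 20 and power is unchanged. If they come on top of it:

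| Further loss per arm | n | Power, SD 20 | Power, SD 15 |
|---|---|---|---|
| 0 | 20 | 75.1% | 94.8% |
| 1 | 19 | 72.6% | 93.6% |
| 2 | 18 | 70.0% | 92.2% |

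**4. Possible bias.** The documents give no removal rate, so these are illustrations, not bounds. Assumptions: 20 per arm, normally distributed changes, SD 15 to 19 (the range cited in 8.0), a complete-case week 52 comparison, and loss from one arm only. Expected normal order statistics for n = 20 are −1.867 SD (lowest) and −1.408 SD (second lowest).

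- Lowest one lost: 1.867 / 19 = 0.098 SD, or 1.5 to 1.9 points.
- Lowest two lost: (1.867 + 1.408) / 18 = 0.182 SD, or 2.7 to 3.5 points.

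These two lines suppose that inability tracks outcome perfectly. With correlation ρ the expected shift is ρ times as large:

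| Lost from one arm | ρ = 0.3 | ρ = 0.5 |
|---|---|---|
| One | 0.44 to 0.56 | 0.74 to 0.93 |
| Two | 0.82 to 1.04 | 1.36 to 1.73 |

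The range is thus about 0.4 to 1.7 points. Against the 16.5-point difference in the 5.5/5.5/22 rows (22 − 5.5) that is 0.44 / 16.5 = 3% to 1.73 / 16.5 = 10%. Two lost in one arm and one in another, at perfect correlation, gives (0.182 − 0.098) SD, about 1.3 to 1.6 points. Equal loss gives about 0.

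**The case against.** The strongest reply is that the bullet means a patient who cannot carry on in the study at all. The protocol is flexible in places: wave speed may be measured in some or all of the listed tasks, treadmill work is only for those used to it (5.3.4), and the faster run in Appendix A depends on ability. That makes an all-or-nothing intention less likely. However, none of this covers strength testing, MRI or ultrasound, and staff have to apply the rule as written.

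Exposure is also small, and this stands. The same procedures are done at week 0, and 4.3.2 already excludes "Inability to comply with study follow-up requirements" and "Contraindication to MRI". Inability would have to be new at week 16.

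The link to outcome is plausible rather than shown, and this stands too. Recording pain after a test does not show that pain prevents it. A sore knee can give a valid but lower reading on a 3 to 5 second isometric effort. Section 5.4 describes no physical risk from ultrasound, and for MRI mainly claustrophobia and positioning discomfort. Only the strength test plausibly carries bias.

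Finally, the shifts depend on a complete-case analysis that the plan does not specify. A model using a removed patient's baseline and any week 16 VISA-P could reduce them.

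A reader might infer that the rule favours PRP. The documents do not support a direction: losing the worst PRP patients would overstate the effect, and losing the worst DN or SH patients would understate it.

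**Conclusion.** The point holds as a defect of wording with a possible consequence. Section 5.6 is mandatory and unlimited in time, it reaches treated patients at week 16 on its literal reading, and no section preserves their later VISA-P scores or side effect logs.

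The likely size is modest. The main cost is precision, and power falls only if removals exceed the two patients per arm already allowed for. Bias needs inability that is both related to outcome and unequal across arms. Under the stated assumptions, one or two patients lost from a single arm shift its mean by about 0.4 to 1.7 points, well below the minimal detectable change of 11.1 cited in 8.0.

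Two stronger readings should be resisted. One is that many patients would be removed: the documents give no rate, and the entry criteria point to few. The other is that data already collected are discarded: Section 7.0 provides for keeping them, and the gap is only that no section says they are analysed.

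**What to change.** For randomised subjects after the baseline treatment session, replace the first bullet of 5.6 with:

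> A subject who cannot complete a follow-up assessment (strength testing, MRI, ultrasound) skips that assessment, the reason is recorded, and the subject stays in follow-up for all other scheduled assessments, including VISA-P/Tegner and the side effect log, unless consent is withdrawn.

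The wording is confined to follow-up assessments on purpose. Section 5.3 also lists PRP preparation and administration among the research procedures, and this change is not meant to govern the treatment session.

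So that the retained data are used, add to 8.0:

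> Randomised subjects are analysed in their assigned group using all available VISA-P data, including data collected before any withdrawal.

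The cost is protocol wording only, with no added visits, staff or patients. The downside is that some subjects will have partial imaging or strength data, so the correlations in aim 3.1.3 will rest on fewer subjects than the VISA-P comparison. Removing those subjects would not recover the missing measurements.
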